### 8.1.2 Statistical Methods Overview

Data collected in this study will be presented using summary tables, data listings and graphs. Study endpoints and parameters will be summarized using descriptive statistics.

The descriptive statistics for continuous variables will include mean, standard deviation, median, Q1 and Q3, minimum, maximum, and sample size. Categorical variables will be described with counts, percentages, and sample size.

For comparison (between arms or against null values), categorical variables will be tested using appropriate contingency table analyses (exact or chi-square approximations), and continuous variables will be tested using Student's t-test or non-parametric methods, depending on variable distribution. P-values will be presented to three decimal places and p-values less than .001 will be presented as '<.001.'

**Study Title:** Multi-site Anesthesia randomized controlled Study of End tidal control (Et Control) compared to conventional anesthesia Results (MASTER-Anesthesia Trial)  
**Study No:** 123.07-2015-GES-0002

GE Healthcare

Subjects using different anesthetic agents will be pooled for analysis per the arm they are randomized. Separate analysis may be performed by anesthetic agent when pooling data across anesthetic agents is not appropriate.

No imputation will be performed for missing data unless specified otherwise.

A data extraction algorithm is used to identify periods of end tidal concentration measurement stability following setting changes (i.e. Steady States) during a case, as well as to measure response times, settling times, and overshoot amounts from these steady states in order to compare across arms. The extraction algorithm is not part of the statistical analysis, but provides the above-mentioned endpoints. (See Appendix 2 – Extraction algorithm for more information on the extraction algorithm.)

There will be two scenarios in defining a step change and steady state when performing the data extraction: 1) *using the data extraction algorithm to determine the desired end-tidal concentrations of anesthetic agent and oxygen for both arms* (See Appendix 2 – Extraction algorithm for more information on the extraction algorithm); 2) *using the clinicians recorded end tidal target values of anesthetic agent and oxygen for the Control arm, and the set target value for the Et Control arm.*

Hypothesis tests will be performed on the following endpoints in the order they are listed: the primary endpoints, ie, percent duration with EtAA and EtO2 maintained within the acceptable range; agent usage; user setting interaction; and time to OR discharge. The sequential approach will be used to control the overall type I error. The next hypothesis and thereafter will not be tested unless the prior null hypothesis is rejected.

#### 8.1.2.1 Analysis Sets

The study analysis sets include the intent-to-treat (ITT) population, evaluable population, per-protocol population, and safety population; and are defined as follows:

- Intent-to-treat (ITT) Population includes all randomized subjects.
- Evaluable Population includes all randomized subjects with at least 45 minutes of inhalation anesthesia data collected during the procedure.
- Per-Protocol Population includes all subjects in evaluable population without critical protocol deviation.
- Safety Population includes all randomized subjects, who underwent anesthesia using the investigational device or the control device.

#### 8.1.3 Analysis of Primary Endpoints

Separate analysis of primary endpoints will be performed on the basis of the extracted data for the following scenarios: 1) *using the algorithm to determine the desired end-tidal concentrations of anesthetic agent and oxygen for both arms; and 2) using the clinicians*

**Study Title:** Multi-site Anesthesia randomized controlled Study of End tidal control (Et Control) compared to conventional anesthesia Results (MASTER-Anesthesia Trial)  
**Study No:** 123.07-2015-GES-0002

GE Healthcare

*recorded target values of anesthetic agent and oxygen for the Control Arm and using the set target values for the Et Control Arm.*

Analysis of primary endpoints will be based on ITT population, evaluable population, and per protocol population. The conclusion will be based on the ITT population.

For EtAA and EtO2 respectively, percent duration with EtAA and EtO2 maintained within the acceptable range will be calculated for each steady state. And the per subject weighted average of the percent duration will be calculated for each subject using the duration of each steady state as the weight.

Using t-test, comparison of the weighted average percent duration between the Et Control and control device will be performed by calculating the difference and its 95% 2-sided confidence interval between the two arms. Non-inferiority will be concluded if the lower limit of the 95% confidence interval is  $\geq -5\%$  for both EtAA and EtO2, and superiority will be concluded if the lower limit of the 95% confidence interval is  $> 0$  for EtAA and the lower limit of the 95% confidence interval is  $\geq -5\%$  for EtO2.

The primary analysis for the primary endpoints consists of the analysis on ITT population based on the algorithm determined end-tidal concentration (scenario 1) and clinician's recorded set target end-tidal concentration (scenario 2). This primary analysis will also be performed for patients of different ASA status.

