## 5. STUDY SUBJECTS

### 5.1 Number of Subjects

A total of 248 Subjects will be enrolled in the study, with approximately 124 subjects enrolled in each arm: Et Control Arm and Control Arm. A minimum of 15 subject cases is the target enrollment for each of the 3 anesthesia agents (Desflurane, Sevoflurane, and Isoflurane) per arm (*only one inhalation anesthetic agent may be used for each enrolled subject in the study arm*).

The study will be conducted at 4 hospitals (investigational sites) located within the United States. Each investigational site is to enroll a minimum of 30 to a maximum of 80 subjects with approximately 1:1 ratio for subject in the Et Control Arm and Control Arm.

Each Investigator will be performing a minimum of five (5) cases for each arm (Et Control and Control). In situations where the Investigator is unable to complete a minimum of 5 cases in each arm, a Sponsor exception may be obtained. Subjects will be randomized to the Et Control Arm or the Control Arm, and randomization will be stratified based on Investigator, subject's pre-existing hypertension status, and subject's ASA status.

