## 6. PROCEDURES FOR RESEARCH STUDY

### 6.1 Randomization and Enrollment

Subjects will be randomized at a ratio of 1:1 to either the "Investigational Et Control Arm" or the "Control Arm." Stratified randomization will be used based on Investigator, subject's pre-existing hypertension status, and subject's ASA status. Randomization sequences will be

**Study Title:** Multi-site Anesthesia randomized controlled Study of End tidal control (Et Control) compared to conventional anesthesia Results (MASTER-Anesthesia Trial)  
**Study No:** 123.07-2015-GES-0002

GE Healthcare

assigned through the IVRS/IWRS system. Subjects will be considered enrolled after providing written informed consent.

The following devices will be employed for each arm of the study:

- ♦ **Investigational Et Control Arm:** legally marketed Aisys CS anesthesia machine with investigational Et Control option
- ♦ **Control Arm:** legally marketed Aisys CS anesthesia machine without the investigational Et Control option

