So the hypotheses on the primary endpoints are:

$$H_0: \mu_{\text{et}} - \mu_{\text{con}} < -5\% \text{ vs } H_1: \mu_{\text{et}} - \mu_{\text{con}} \geq -5\%$$

**Study Title:** Multi-site Anesthesia randomized controlled Study of End tidal control (Et Control) compared to conventional anesthesia Results (MASTER-Anesthesia Trial)  
**Study No:** 123.07-2015-GE5-0002

GE Healthcare

for both EtAA and EtO2, where  $\mu_{et}$  is the percent duration of Et Control with EtAA and EtO2 maintained within the acceptable range, and  $\mu_{con}$  is the percent duration of control device with EtAA and EtO2 maintained within the acceptable range.

Both null hypotheses have to be rejected for EtAA and EtO2 to conclude non-inferiority. So the alpha is set at 0.025 one-sided with no need for multiplicity adjustment, but the power for each hypothesis is set at 0.95 to have an overall power of 0.9 for the study. And the larger sample size calculated for EtAA and EtO2 will be the size of the study.

The results from the feasibility study on the weighted average of percent duration with EtAA and EtO2 maintained within the acceptable range is listed below. The difference between Et Control and control device is assumed to be 50% less than what was observed, and the larger standard deviation observed is used in sample size calculation using the 2-sample t-test method.

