### 8.3 Handling of Missing Data

In general, data analysis will be performed on the basis of all available data.

For missing values of primary endpoints, multiple imputations will be performed and sensitivity analysis will be conducted for primary endpoints. The multiple imputation will be performed with SAS PROC MI, using the regression method for monotone missing pattern, with the covariates treatment arm, clinician, anesthetic agent, and subject ASA status as the independent variables. A total of 5 imputed data sets will be generated and analysis of primary endpoints will be performed on each imputed data set. PROC MIANALYZE will be used to summarize the results from imputed data sets.

Clinician recorded end tidal target values are considered missing, when a recorded target is not available for a setting adjustment resulting in a significant change in end tidal measurements. If the change in end tidal measurement results in more than 5% v/v O2, 0.9% v/v DES, 0.31% v/v SEV, or 0.15% v/v ISO from the previous end tidal measurement over a period of 2 minutes, then the recorded target data is considered missing. This portion of the data is not used for the purpose of the analysis with the clinician recorded target values.

**Study Title:** Multi-site Anesthesia randomized controlled Study of End tidal control (Et Control) compared to conventional anesthesia Results (MASTER-Anesthesia Trial)  
**Study No:** 123.07-2015-GE5-0002

GE Healthcare

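### The deciding primary comparison is an unadjusted t-test although randomisation is stratified by investigator, hypertension and ASA, so precision is lost if those factors predict percent duration

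*Combined protocol and SAP*

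**What the plan says.** Section 6.1: "Stratified randomization will be used based on Investigator, subject's pre-existing hypertension status, and subject's ASA status". Sections 3.2 and 5.1 and the synopsis repeat this.

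Section 8.1.3 gives the deciding analysis: "Using t-test, comparison of the weighted average percent duration between the Et Control and control device will be performed by calculating the difference", with a two-sided 95% confidence interval in the ITT population. Non-inferiority needs a lower limit of at least −5% for both EtAA and EtO2. Superiority needs an EtAA lower limit above 0 with EtO2 non-inferior. No covariate is named. The repeat by ASA status in the same section is a subgroup analysis, not an adjustment. Section 8.1.2 offers nothing further for continuous variables: "t-test or non-parametric methods, depending on variable distribution".

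The sample size in section 8.1.1 uses the same method: "the larger standard deviation observed is used in sample size calculation using the 2-sample t-test method".

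Prognostic factors appear only in the multiple-imputation model of section 8.3: "with the covariates treatment arm, clinician, anesthetic agent, and subject ASA status as the independent variables". Hypertension is missing from that list. Clinician is defined in section 1.1.1 to include residents, fellows and nurse anesthetists, whereas randomisation uses the investigator.

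**The concern.** Stratified randomisation pushes the arms towards balance on the three factors. If the factors predict percent duration, the real variability of the arm difference falls, but the t-test still counts the between-stratum variation in its standard error. The interval is then wider than the data justify and covers more than its nominal 95%.

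It is plausible that the factors matter. Section 1.1.3 describes conventional practice as depending on the clinician's repeated vaporizer adjustments, and section 8.3 already treats clinician and ASA as predictors of the primary endpoint. The size of the effect is not given.

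The lower confidence limit decides pass or fail (section 8.4). The same gate must be passed before agent usage, user interactions and time to OR discharge can be tested (section 8.1.2), and the EtAA limit also decides the superiority claim. Needless width makes each of these harder to reach, most of all if the true difference is smaller than planned.

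**Working it through.** **Inputs from the documents.** One-sided alpha 0.025, power 0.95 per endpoint, margin 5 points, 15% dropout (section 8.1.1). EtAA 87 v 90, SD 16; EtO2 81 v 89, SD 19 (Table 8-1).

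**Assumed.** R², the share of outcome variance explained by the three factors, 0 to 0.30; 8 or 20 investigators; blocks of 4; hypertension 40%; ASA 20/50/30%; half of R² from investigator and half from hypertension and ASA. Section 5.1 asks for at least 5 cases per arm per investigator, exceptions allowed. So 248/10 gives at most about 24 investigators, and up to 24 × 2 × 3 = 144 strata. Full balance therefore cannot be taken for granted.

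**Step 1: reproduce the plan's figures.** Two-sample non-inferiority t-test (noncentral t).
- EtAA: distance 5 + 3 = 8, SD 16 gives 105 per arm; 105/0.85 = 123.5, so 124.
- EtO2: distance 5 + 8 = 13, SD 19 gives 57 per arm; 57/0.85 = 67.1, so 68.

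Both match Table 8-1.

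**Step 2: formula under perfect stratum balance and no fitting cost.** Half-width = t × SD × √(1 − R²) × √(2/n), with R² = 0 for the t-test. EtAA, 105 per arm: 1.971 × 16 × √(2/105) = 4.35.

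| R² | EtAA, 105/arm | EtAA, 124/arm | EtO2, 124/arm | True one-sided error of the t-test |
|---|---|---|---|---|
| 0 (= t-test width) | 4.35 | 4.00 | 4.75 | 0.025 |
| 0.10 | 4.13 | 3.80 | 4.51 | 0.019 |
| 0.20 | 3.89 | 3.58 | 4.25 | 0.014 |
| 0.30 | 3.64 | 3.35 | 3.98 | 0.010 |

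**Step 3: simulation with blocked, imperfect balance.** EtAA, 105 per arm, SD 16, additive effects, 3,000 trials per setting. The model has arm, ASA, hypertension and a random intercept for investigator (REML). Ranges cover 8 and 20 investigators. Monte Carlo error is about 0.004 on coverage and on power near 0.95.

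| R² | Half-width, t-test v model | t-test coverage | Power at +3, t-test v model | Power at 0, t-test v model |
|---|---|---|---|---|
| 0 | 4.35 v 4.34 | 94–95% | about 0.95 for both | 0.61–0.63 for both |
| 0.10 | 4.35 v 4.14–4.17 | 96% | 0.956–0.966 v 0.967–0.970 | 0.62–0.64 v 0.66 |
| 0.30 | 4.36 v 3.66–3.71 | 97.0–97.6% | 0.965–0.978 v 0.988–0.991 | 0.63 v 0.76 |

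Adding arm-specific residual variances (500 trials per setting) gives almost the same widths: 4.35 v 4.34–4.35, 4.33–4.34 v 4.14–4.17, and 4.31–4.34 v 3.65–3.72. Model coverage was 0.93–0.95 (Monte Carlo error about 0.01).

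**Step 4: EtAA superiority at +3.** With 105 per arm and perfect balance, power of t-test v model is 0.27 for both at R² 0, 0.26 v 0.30 at 0.10, and 0.23 v 0.36 at 0.30. The t-test loses superiority power as R² rises because its interval over-covers.

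**Step 5: how the model is fitted matters.** Twenty fixed investigator effects with HC3 standard errors are wider than the t-test at R² 0 (4.75 v 4.34) and at 0.10 (4.51 v 4.36), and narrower only by 0.20 (4.26 v 4.36). With ordinary standard errors, 20 fixed effects still cost width at R² 0 (4.48 v 4.35).

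**Step 6: effects that differ by arm.**
- Investigator effects in the Control arm only, 30% of its variance (1,200 trials): 4.01 v 3.86–3.89.
- SDs of 8 and 18, with stratum effects scaled to each arm's SD, R² 0.30: 3.76–3.78 v 3.31–3.36. Superiority power is about 0.33 v 0.42–0.43.

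**The case against.** The strongest reply is that nothing is broken. Design and analysis match: the trial was sized with the total SD for the t-test that it will use, the stated sizes reproduce exactly, and a conservative interval costs only the sponsor. That stands, and it limits the point to lost precision.

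Second, the documents give no evidence on R². At 0.10 the gain is small, and a sizeable one appears only near 0.30. That also stands.

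Third, the feasibility data in section 1.2.3 show SDs of 7.92 (Et Control) and 18.02 (Control), with the device arm near its ceiling. Stratum effects may therefore be confined largely to the Control arm, where the gain is small. With those SDs the unadjusted half-width at 105 per arm is 1.98 × √((7.92² + 18.02²)/105) = 3.80, and power is 0.985 at +3 and 0.73 at 0. So there may be more power in hand than Table 8-1 implies, although these SDs come from 28 subjects. If the effects instead scale with each arm's SD, the gain persists (step 6).

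Fourth, adjustment is not free in every form. Many fixed investigator effects can widen the interval, and a mixed model needs rules on pooling and degrees of freedom. This is right about fixed effects. The random intercept with arm-specific variances showed essentially no cost at R² 0, and the extra rules are ordinary analysis-plan text.

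**Conclusion.** The concern holds as a conditional loss of precision. The comparison that decides the trial ignores all three stratification factors. If they explain 10% to 30% of the variance in percent duration, the t-test half-width for EtAA is about 4.35 where a suitable model gives about 4.15 to 3.7. If they explain nothing, nothing is lost.

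At the planned +3 the power gain for non-inferiority is at most about 2 points. It is larger for a true difference near 0 (0.63 to 0.76 at R² 0.30) and for superiority (0.23 to 0.36 at R² 0.30). These sizes rest on an assumed R², additive effects, SD 16 in both arms and the assumed investigator count and case mix. If only the Control arm carries investigator effects, the gain is small.

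The stated power and the validity of a non-inferiority conclusion are not in question. The change should be made, but it is not a condition for the trial to be interpretable. Separately, the imputation model should match the randomisation factors. That is a matter of wording, and I have put no size on it.

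**What to change.** - **Section 8.1.3:** make the primary estimate the arm difference and 95% interval from a prespecified linear model of per-subject percent duration on arm, ASA status, hypertension and investigator. Fit investigator as a random intercept, or pool small investigators within site by a stated rule. Do not fit about 20 fixed investigator effects.
- Allow unequal variance by arm, through arm-specific residual variances or heteroscedasticity-robust standard errors. State the degrees-of-freedom method and the fallback if the model does not converge.
- Apply the same −5% and 0 rules, and keep the t-test as a sensitivity analysis.
- **Section 8.3:** add hypertension to the imputation model and use the investigator as randomised in place of clinician. Combine the model estimates across the imputed data sets.
- Fix the wording before outcome data are reviewed, because clinicians and investigators are unblinded (section 4.2).

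The cost is analysis-plan text, including the pooling and fitting rules above. All three factors are already needed for randomisation, and the sample size does not change.

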#### **8.1.4 Analysis of Secondary Endpoints**

##### **8.1.4.1 Performance Statistics**

For response time, settling time and overshoot amount (% to steady state mean for anesthetic agent, and v/v for O2), analysis will be on the basis of each steady state. The arithmetic average of all steady states will be calculated and be compared between the Et Control Arm and the Control Arm using t-test. Subjects with at least 1 overshoot amount greater than 10%, 20%, or 30% of steady state concentration will be counted and compared between the two arms using Fisher exact test.

For average deviation (% to steady state mean for anesthetic agent, and v/v for O2) and half width of 95% CI of deviation, analysis will be on the basis of each subject. The weighted average using the duration of steady state duration as the weight for a subject will be calculated and compared between the Et Control and Control Arms using t-test. For the maximum deviation (% to steady state mean for anesthetic agent, and v/v for O2), the maximum of all steady states for a subject is taken for analysis, and the maximum deviation be compared between Et Control and Control arms using nonparametric Wilcoxon rank sum method.

The analysis of above performance statistics will be performed by different ASA status.

**Study Title:** Multi-site Anesthesia randomized controlled Study of End tidal control (Et Control) compared to conventional anesthesia Results (MASTER-Anesthesia Trial)  
**Study No:** 123.07-2015-GES-0002

GE Healthcare

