## 3.4 Study Endpoints

### 3.4.1 Primary Endpoint:

- (1) Percent duration without large deviation of EtAA:

Percent duration of EtAA concentration during steady state maintained within the acceptable limit, which is defined as the greater of 5% of the steady state inhaled anesthetic agent concentration and 0.6% v/v for Desflurane (Des), 0.2% v/v for Sevoflurane (Sev), or 0.1% v/v for Isoflurane (Iso). The percent duration is the weighted average of all steady states for a subject, using the duration of steady state as the weight. It is expressed as:

**Study Title:** Multi-site Anesthesia randomized controlled Study of End tidal control (Et Control) compared to conventional anesthesia Results (MASTER-Anesthesia Trial)  
**Study No:** 123.07-2015-GE5-0002

GE Healthcare

$$PercentDuration = \frac{\sum_j \sum_i t_{ij} I_{ij}}{\sum_j T_j} \times 100\% \quad \text{where } t_{ij} \text{ is the } i^{\text{th}} \text{ duration of EtAA concentration}$$

maintained within the acceptable limit during the  $j^{\text{th}}$  steady state, and  $T_j$  is the total duration of the  $j^{\text{th}}$  steady state.  $I_{ij}$  is an indicator for whether EtAA is maintained within the acceptable limit of  $i^{\text{th}}$  duration in  $j^{\text{th}}$  steady state, which is

$$I = \begin{cases} 1 & \begin{array}{l} \text{if Desflurane and } \Delta EtAA \leq \max(0.6\%, 5\%X \text{ steady state EtAA}) \\ \text{if Sevoflurane and } \Delta EtAA \leq \max(0.2\%, 5\%X \text{ steady state EtAA}) \\ \text{if Isoflurane and } \Delta EtAA \leq \max(0.1\%, 5\%X \text{ steady state EtAA}) \end{array} \\ 0 & \text{otherwise} \end{cases}$$

$\Delta EtAA$  is the absolute difference between measured EtAA concentrations and steady state EtAA concentration.

(2) Percent duration without large deviation of  $EtO_2$ :

Percent duration of  $EtO_2$  concentration during steady state maintained within the acceptable limit, which is defined as 5% v/v. This definition is similar to that of the EtAA, except that the acceptable limit is set as 5% v/v.

**NOTE:** The steady state concentration is based on extraction algorithm for both Et Control and Control arms as well as based on the clinician's recorded target values for the Control Arm and the set target values for the Et Control Arm.

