These two primary endpoints, along with the secondary efficacy endpoints (response time, setting time, overshoot amount), are chosen to assess the capability of Et Control in achieving and maintaining the end tidal concentration of anesthetic agent and oxygen.

This study is designed to demonstrate that Et Control is non-inferior to the control device in maintaining end tidal anesthetic agent (EtAA) and end tidal oxygen ( $EtO_2$ ) concentrations by a margin of 5%.

The hypotheses for the primary endpoints are:

$$H_0: \mu_{\text{et}} - \mu_{\text{con}} < -5\% \text{ vs } H_1: \mu_{\text{et}} - \mu_{\text{con}} \geq -5\%$$

for both EtAA and  $EtO_2$ , where  $\mu_{\text{et}}$  is the average percent duration of Et Control with EtAA and  $EtO_2$  maintained within the acceptable range, and  $\mu_{\text{con}}$  is the average percent duration of control device with EtAA and  $EtO_2$  maintained within the acceptable range.

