### 8.1.5 Et Control Accuracy

To assess the accuracy of Et Control in maintaining the target EtAA and EtO2 concentrations for each steady state, both mean absolute difference and mean percent difference between measured Et concentrations of AA and the setting values will be calculated, and the mean differences will be summarized for all steady states using descriptive statistics and 95% confidence intervals for each anesthetic agent and overall. The same accuracy analysis will be performed for EtO2. The mean differences will also be plotted against the setting values to assess consistency across the concentration range for each anesthetic agent. Percent of time duration in a steady state will also be assessed; when the percent difference exceeds 5%, 10%, and 15% of the setting values.

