- 4) Determine the desired end tidal concentration by averaging all EtAA or EtO2 points once stability is reached until the next significant setting change. Non-significant changes are ignored and treated as part of the current step change/steady state.
- 5) For all significant changes which reach a stable concentration, compute the efficacy performance statistics (Response Time, Command Overshoot, Settling Time, Steady State Mean and Standard Deviation).
  - a. Response Time for agent is defined as the smaller of either the time to reach 90% of the change between the initial EtAA and the desired end tidal concentration or the

**Study Title:** Multi-site Anesthesia randomized controlled Study of End tidal control (Et Control) compared to conventional anesthesia Results (MASTER-Anesthesia Trial)  
**Study No:** 123.07-2015-GES-0002

GE Healthcare

time to get to within 0.9 %v/v, 0.31 %v/v or 0.17 %v/v for DES, SEV or ISO, respectively, of the desired end tidal concentration.

- b. Response Time for oxygen is defined as the smaller of either the time to reach 90% of the change between the initial EtO2 and the desired end tidal concentration or the time to get to within 5 %v/v of the desired end tidal concentration.
- c. Command Overshoot is defined as the maximum value beyond the desired end tidal concentration from the start of the step change until the Settling Time.
- d. Settling Time for agent is determined by looking backwards from the stable concentration to the time where the agent is within 0.9 %v/v, 0.31 %v/v and 0.17 %v/v for DES, SEV and ISO, respectively, of the desired end tidal concentration.
- e. Settling Time for oxygen is determined by looking backwards from the stable concentration to the time where the oxygen is within 5 %v/v of the desired end tidal concentration.

**Study Title:** Multi-site Anesthesia randomized controlled Study of End tidal control (Et Control) compared to conventional anesthesia Results (MASTER-Anesthesia Trial)

**Study No:** 123.07-2015-GES-0002

GE Healthcare

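### As written, response time, settling time, overshoot and accuracy are analysed per steady state, with no allowance for several steady states from one subject

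*Combined protocol and SAP*

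**What the plan says.** For response time, settling time and overshoot, section 8.1.4.1 states that "analysis will be on the basis of each steady state", and continues: "The arithmetic average of all steady states will be calculated and be compared between the Et Control Arm and the Control Arm using t-test". The next paragraph, on average deviation and the half width of its confidence interval, changes the unit: "analysis will be on the basis of each subject". Maximum deviation is also reduced to one value per subject. Section 8.1.3 does the same for the primary endpoints: "the per subject weighted average of the percent duration will be calculated for each subject".

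In section 8.1.5 a mean difference from the set value is calculated for each steady state in the Et Control arm. Then "the mean differences will be summarized for all steady states using descriptive statistics and 95% confidence intervals", by agent and overall.

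The documents expect more than one steady state per subject. Section 3.4.1 defines the primary percent duration as "the weighted average of all steady states for a subject". Appendix 2, step 5, reads: "For all significant changes which reach a stable concentration, compute the efficacy performance statistics".

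Sections 8.1.2 to 8.1.5 contain no random effect, clustered variance or other within-subject term, and none appears elsewhere in the plan.

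**The concern.** The subject is the randomized unit. Steady states from one case share the patient, the clinician and the agent, so they are likely to resemble each other. A two-sample t-test over all steady states in an arm counts each as a separate, independent observation. Its standard error is then too small whenever the within-subject correlation is positive. The same holds for a confidence interval computed over all steady states. Pooling also gives more weight to subjects with more setting changes, and that number arises after randomization.

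These results have a visible role. Section 3.4.1 says of the two primary measures that they, "along with the secondary efficacy endpoints (response time, setting time, overshoot amount), are chosen to assess the capability of Et Control". Section 3.1 says the study supports a US marketing application. Section 8.1.4.1 repeats the performance analyses by ASA status, so the subgroup p-values would carry the same error.

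**Working it through.** **Which unit the text names.** Two adjacent paragraphs of 8.1.4.1 name different units, first the steady state and then the subject. Where a per-subject reduction is meant (average deviation, maximum deviation, the primary endpoints), the plan says so. For response time, settling time and overshoot it does not. The steady state is therefore the plain reading. Section 8.1.5 never mentions a per-subject step.

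**The plan's own figures.** None is given for these endpoints. The sample size in Table 8-1 belongs to the subject-level primary endpoints. It reproduces with a two-sample t calculation at one-sided alpha 0.025 and power 0.95:
- EtAA: distance to the margin 5 + 3 = 8, SD 16, gives 105 per arm; 105/0.85 = 123.5, so 124 (stated 124).
- EtO2: distance 5 + 8 = 13, SD 19, gives 57 per arm; 57/0.85 = 67.1, so 68 (stated 68).

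These figures are not affected. They supply the 105 subjects per arm used in the simulation below.

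**Inputs that must be assumed.** The documents do not give the number of steady states per subject (m) or the intraclass correlation (ICC), and they set no alpha for these tests. I take m = 3 to 8, ICC = 0.1 to 0.3 and a two-sided 5% level.

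**Formulas.** Design effect DE = 1 + (m − 1) × ICC. The standard error is understated by a factor of √DE. True two-sided type I error = 2 × (1 − Φ(1.96/√DE)). Coverage of a nominal 95% interval is 1 minus that value.

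For m = 5 and ICC = 0.2: DE = 1 + 4 × 0.2 = 1.80, √1.80 = 1.34, 1.96/1.34 = 1.46, and 2 × (1 − Φ(1.46)) = 14.4%.

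| m | ICC | DE | SE factor | Type I error | Coverage |
|---|---|---|---|---|---|
| 3 | 0.1 | 1.20 | 1.10 | 7.4% | 92.6% |
| 3 | 0.3 | 1.60 | 1.26 | 12.1% | 87.9% |
| 5 | 0.1 | 1.40 | 1.18 | 9.8% | 90.2% |
| 5 | 0.2 | 1.80 | 1.34 | 14.4% | 85.6% |
| 5 | 0.3 | 2.20 | 1.48 | 18.6% | 81.4% |
| 8 | 0.3 | 3.10 | 1.76 | 26.6% | 73.4% |

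**Simulation check** (20,000 runs, 105 subjects per arm, no true difference). In the settings (3, 0.1), (5, 0.2) and (8, 0.3), the pooled t-test rejected in 7.0%, 14.8% and 27.0% of runs when every subject had the same m. It rejected in 8.3%, 15.9% and 29.0% when m varied between subjects as 1 + Poisson(m − 1). A t-test on one mean per subject rejected in 4.5% to 5.3% of runs in all six settings.

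**Zero-effect cases.** If m = 1 or ICC = 0, then DE = 1 and nothing changes.

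**The case against.** The strongest reply is that the disputed sentence can be read another way. It says an average is formed and then compared, and the parallel sentence on deviation speaks of a weighted average. The contrast might be unweighted versus duration-weighted averaging within a subject, because a response time belongs to a step and has no natural duration weight. On that reading the t-tests are sound. This possibility stands, but the sentence just before sets the steady state as the unit, and only the deviation paragraph says the average is for a subject. Two statisticians could run different tests from this text. The reading also does nothing for 8.1.5.

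The size of the effect is not anchored in the documents. Section 1.2.3 reports about 26 setting interactions per case in the feasibility study, which makes several steps per subject plausible. It does not fix m, because Appendix 2 merges non-significant changes. Steps within a case may differ in size and direction, so the ICC could be low. The 27% error and 73% coverage are the worst corner of an assumed grid, and the simulation only confirms the formula under those assumptions. This stands.

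The consequences are limited, and this also stands. These endpoints lie outside the ordered tests in 8.1.2 and the pass/fail rule in 8.4, and the plan announces no claim on them. Section 8.1.5 is a single-arm summary with no test or acceptance limit. The overshoot counts compared by Fisher's exact test are already per subject.

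**Conclusion.** The concern holds for the plan as written. Section 8.1.4.1 names the steady state as the unit for three secondary efficacy endpoints, section 8.1.5 runs its confidence intervals over all steady states, and nothing allows for repeated steady states within a subject. If there are several per subject and they correlate positively, the p-values would be too small and the accuracy intervals too narrow. The illustrative range is a true type I error of about 7% to 27% at nominal 5%, and coverage of about 93% to 73% at nominal 95%. It rests wholly on the assumed m and ICC. The size is uncertain, but the direction is not. Only supportive results are affected; the trial's formal conclusions do not change. If a per-subject average is intended in 8.1.4.1, the defect there is one of wording, and 8.1.5 still needs a stated method.

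**What to change.** In 8.1.4.1, state the unit of analysis for response time, settling time and overshoot, then choose one option:

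- **Per-subject question:** average the steady states within each subject and apply the t-test to one value per subject, as is already planned for average deviation (there with duration weights).
- **Per-step question:** keep every steady state, and use subject-clustered standard errors or a mixed model with a random subject intercept.

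In 8.1.5, compute the 95% intervals from subject-level means or with subject-clustered standard errors. Subject means are the safer choice for the by-agent intervals. Section 5.1 targets a minimum of only 15 subjects per agent per arm, and ordinary clustered standard errors can be too small with so few clusters.

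Report the number of steady states per subject by arm.

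The cost is SAP wording and a few lines of code, with no new data. Where the correlation is positive, intervals widen somewhat and p-values rise. The first option changes the question from the average step to the average subject, and the plan should say which is meant.
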